28.0 Statistical Analysis*

28.1 We will use two-tailed McNemar's test with paired measures to analyze differences in diagnostic thinking efficacy and therapeutic efficacy from pre- and post-BUS surveys. Comparison of duration of antibiotics, bowel rest, and days to full enteral feeds will be performed using Student's t-test. Kaplan-Meier curve will be used to analyze time to full feeds between the 2 groups, censoring for death, discharge/transfer out of the hospital, or 30 days following initial NEC concern. Analyses of patient outcomes (duration of bowel rest, duration of antibiotics, time to full feeds) will follow the intention-to-treat principle, with statistical significance set at a P value of < 0.05.

28.2 We will use t-test to analyze differences in mean time of BUS image acquisition and reporting. Chi-square test will be used to compare differences in proportion of BUS studies that were performed and reported per standardized protocol. Inter-rater reliability for BUS studies will be assessed by Cohen's kappa statistics.

28.3 Sample size was calculated based on our pilot study which demonstrated a mean \pm SD of duration to full enteral feeds of 16 ± 9 days per episode of NEC concern. Using this information, we generated Table 1, which shows sample sizes for a range of possible means and standard deviations, with significance level of 0.05 and 80% power. For a 1-year study with 67 to 81 distinct episodes, for an SD of +8 days, we anticipate having sufficient sample size to detect a 5- to 6-day difference in mean duration to full feeds (highlighted in gray in Table 1).

Difference of means between groups	Expected Standard Deviation		
	± 8	± 9	± 10
4 days	126	160	198
5 days	81	102	126
6 days	56	72	88

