	
want the information provided. A secondary concern would be the excessive personnel time and cost requirements to consent 222 families to meet the targeted enrollment of 80 infants.
 
(3) The inherent differences in families able to be consented versus not consented in the study may result in underrepresentation, selection bias, reduced generalizability, and erroneous conclusions. In our pilot study, majority of infants were unable to be consented for two reasons. The first reason (40% of infants) was that the infants were very sick at the time of transfer and their NEC concern episode happened very early in their hospitalization, resulting in very limited time to consent the parents. The second reason (also 40% of infants) was that infants were transferred from faraway hospitals. As a level IV NICU, infants admitted at CMH are referred from the whole of Kansas and western half of Missouri. Similarly, as a tertiary referral hospital for high-risk pregnancies, KUMC admits and delivers pregnant moms from all over Kansas. Such families who live farther away from Kansas City are often not able to be present as often in the NICU to be approached for research. Thus, because of these two reasons for limited availability to obtain consent, we believe our pilot study sample was biased by overrepresentation of healthier infants and infants from the Kansas City metropolitan area. Limited availability to consent for research is also known from prior studies to be higher among families that have transportation issues, speak a different language other than English or Spanish, unable to pay their phone bills, etc. Together, these barriers can systematically prevent the inclusion of at-risk families in research studies, decreasing generalizability of our results. If this selection bias were to persist in our larger study, it would weaken the scientific validity of our research by increasing the likelihood of missing important benefits or hazards and reaching erroneous conclusions.

--	---

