(4) **Complexity of following consented infants for development of NEC concern result in missed randomization, loss of study participants, and insufficient power.** In our pilot study, 20% of consented infants who developed concern for NEC (4/20) were not randomized into the study. The complexity of following consented infants prospectively for development of NEC concern is a major contributing factor for missed randomization. This is because NEC concern, which by itself is already a relatively rare event, can occur at any time of the day or night, and can occur several weeks from the time of informed consent. The loss of even a few subjects from complex consent process and missed randomization would negatively impact the power and validity of our proposed study. Instead, we propose including all consecutive infants who develop NEC concern into the study with waiver of consent to simplify the study process, eliminate errors related to missed randomization, and maximize sample size and power for the study.

[figure not shown]

Figure 3. A hypothetical example of 100 eligible patients to demonstrate how traditional consent process prior to NEC concern is not practicable. Using estimates based on our pilot study, the traditional consent process would have only successfully randomized 13 infants (green box). The red boxes indicate reasons why the traditional consent process would not be practicable for our study. In contrast, a waiver of informed consent would have successfully randomized 36 infants (green box + yellow boxes).

SHORT TITLE: BUS for NEC

If the research involves using identifiable private information or identifiable biospecimens, the research could not practicably be carried out without using such information or biospecimens in an identifiable format	PHI is required to identify subjects and data from all participants is needed to describe aims of the study.

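### The 5- to 6-day detectable difference in section 28.3 rests on an SD of 8, below the pilot's own 9, and the pilot was a consented sample that the protocol itself believes was healthier than the population to be enrolled

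*Combined protocol and SAP*

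**What the plan says.** Section 28.3 takes the variability of the sizing outcome from the pilot: "Sample size was calculated based on our pilot study which demonstrated a mean" and "SD of duration to full enteral feeds of 16 ± 9 days per episode of NEC concern". Table 1 gives total sample sizes for SDs of 8, 9 and 10, "with significance level of 0.05 and 80% power". The conclusion uses only the smallest: "for an SD of +8 days, we anticipate having sufficient sample size" to detect 5 to 6 days, with 67 to 81 episodes in a 1-year study. Section 28.1 says that comparison of "days to full enteral feeds will be performed using Student's t-test".

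Addendum B, which justifies the waiver of parental permission, describes the same pilot. Item (3) says that the investigators believe the sample "was biased by overrepresentation of healthier infants and infants from the Kansas City metropolitan area". For 40% of the infants who could not be consented, the reason was that "the infants were very sick at the time of transfer and their NEC concern episode happened very early in their hospitalization". Item (4) describes the remedy: "we propose including all consecutive infants who develop NEC concern into the study with waiver of consent".

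The documents give three sizes. Section 28.3 has 67 to 81 episodes in 1 year, Addendum B item (2) has a target of 80 infants over 2 years, and section 8.0 has a goal of 200 neonates (120 + 80).

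**The concern.** There are two gaps, and they differ in strength.

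- **SD 8 instead of 9.** The stated detectable difference uses an SD smaller than the one the pilot observed, with no reason given. This can be checked from the plan's own figures.
- **Change of population.** The protocol uses the pilot's selection to argue for the waiver, but section 28.3 does not say whether the pilot SD carries over to unselected infants. Adding a sicker group with longer courses would normally widen the spread of days to full feeds.

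The stake is how the result is read. If the trial has well under 80% power for 5 days, a null result could be taken as excluding a benefit that the trial could easily have missed.

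**Working it through.** **Inputs.** Alpha 0.05, power 80%, SDs of 8, 9 and 10, and 67 to 81 episodes (all section 28.3); Student's t-test (section 28.1). Sidedness and allocation ratio are not stated for this outcome. I assume two-sided and 1:1, which reproduce Table 1. I also assume independent episodes and no dropout.

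**Step 1: reproduce Table 1.** Total N = 4 × SD² × (1.960 + 0.842)² / d², where d is the difference in means.
- d = 5, SD 8: 4 × 64 × 7.85 / 25 = 80.4. Table 1 has 81.
- d = 5, SD 9: 101.7. Table 1 has 102.
- d = 6, SD 9: 70.6, or 36 per arm. Table 1 has 72.
- With rounding up per arm, eight of the nine cells match exactly. The ninth is 82 against 81.

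Table 1 is therefore sound, and it already shows the problem. At SD 9 it asks for 102 episodes to detect 5 days and 72 to detect 6. At SD 10 it asks for 126 and 88, both above 81.

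**Step 2: detectable difference at 80% power.** By normal approximation, d = SD × √(4/N) × 2.802. For SD 9 and N = 81, 9 × 0.2222 × 2.802 = 5.60. For SD 9 and N = 67, 9 × 0.2443 × 2.802 = 6.16. The t-test values are slightly larger:

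| SD | N = 81 | N = 67 |
|---|---|---|
| 8 | 5.04 days | 5.56 days |
| 9 | 5.67 days | 6.25 days |
| 10 | 6.30 days | 6.95 days |

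**Step 3: power (t-test).**

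| SD | 5 days, N = 81 | 5 days, N = 67 | 6 days, N = 81 | 6 days, N = 67 |
|---|---|---|---|---|
| 8 | 79.3% | 71.2% | 91.5% | 85.6% |
| 9 | 69.5% | 61.0% | 84.2% | 76.7% |
| 10 | 60.4% | 52.2% | 76.0% | 67.7% |

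**Step 4: could case mix move the SD?** This step is illustrative, because the documents give no mean or SD for the infants the pilot missed. Figure 3's caption has 36 infants with NEC concern per 100 eligible, and 13 randomised through consent. With 20% missed randomisation, 13 / 0.8 = 16.25 were consented and 19.75 were not. If 40% of those were the very sick group, the share is 0.4 × 19.75 / 36 = 0.219. The mixture SD is √[0.781 × 81 + 0.219 × s² + 0.219 × 0.781 × g²], where s is the group's SD and g its extra days (both assumed).
- s = 9, g = 5: SD 9.2
- s = 9, g = 10: SD 9.9
- s = 6, g = 5: SD 8.7

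Reaching SD 10 with s = 9 needs g = √(19 / 0.171), about 10.5 days.

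**Step 5: dependence on N.** If 200 independent values are analysed, the t-test detects 3.6 days at SD 9, 4.0 at SD 10 and 4.8 at SD 12. At 80 the figures are 5.7 at SD 9 and 6.3 at SD 10, almost the same as at 81.

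**The case against.** A reader might infer that SD 9 is demonstrably too small for the new population, that SD 10 is the right planning value, and that the trial is underpowered. The documents do not support any of these.

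- **Direction.** The statement about healthier infants is the investigators' belief about case mix. It says nothing about the variance of feeding times. A less variable sick group could leave the SD at or below 9 (8.7 in Step 4).
- **Share.** The 22% comes from the caption of a hypothetical example. The 40% refers to infants who could not be consented, not specifically to those who then had NEC concern. If the group arises only at CMKC, which supplies 120 of 200, the share is 0.6 × 0.219 = 13%, and a 10-day gap gives SD 9.6.
- **Long courses.** Section 25.1 allows withdrawal after certain surgery. Section 28.1 censors the Kaplan-Meier analysis at 30 days but does not say whether the t-test values are capped. Either could trim the tail.
- **Imprecision.** If about 16 values lie behind the pilot SD (assumed from the 16 of 20 randomised in Addendum B), its 95% interval is roughly 6.7 to 13.9. That is wider than most of the modelled shift.
- **SD 10 is already tabulated.** Table 1 shows it, although the conclusion does not use it.
- **N.** The shortfall belongs to the 67 to 81 episode claim. Against an analysed N of 200 it largely disappears.

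All of this stands against a firm claim about case mix. None of it explains the choice of 8 over 9. Nor does the figure of 200 settle N: section 8.0's form counts infants consented or screened. If the 200 are eligible infants, the pilot's 36% rate gives 200 × 0.36 = 72 with NEC concern, back within 67 to 81.

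**Conclusion.** The point holds in a limited form. The 5- to 6-day statement is optimistic for 67 to 81 episodes because it uses SD 8. At the pilot's own SD of 9 the range is about 5.7 to 6.25 days. Five days is not reached at 80% power anywhere in the range, and 6 days only towards its upper part. At SD 10 the range is about 6.3 to 6.95 days, wholly outside the stated one.

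That the broader population has an SD above 9 is plausible but undocumented in direction and size, so SD 10 is a sensible sensitivity case and not a corrected value. Whether the trial as a whole lacks power cannot be decided until N is settled.

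The figures assume a two-sided test, 1:1 allocation, independent episodes and no dropout. Repeat episodes per infant (section 10.7) and allocation by birth month (section 10.2) are not modelled.

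**What to change.** In section 28.3:

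1. Replace the SD 8 headline with the detectable difference at the pilot SD of 9: about 5.7 days (81 episodes) to 6.25 days (67 episodes).
2. Give SD 10 as the sensitivity case for the broader population: about 6.3 to 6.95 days.
3. State that the pilot SD comes from a consented sample believed to be healthier than the infants to be enrolled.
4. Say which N the claim refers to, and reconcile 67 to 81 episodes in 1 year, 80 infants over 2 years and 200 neonates. If 200 is the number analysed, restate the detectable difference for it.
5. Optionally, calculate the SD once on accrued data with the arms combined, and restate the detectable difference from it.

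The cost is a wording change and, if item 5 is taken up, one calculation on data already collected. No extra enrolment is needed. The only downside is a less favourable stated figure.

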
The research could not practicably be carried out without the requested waiver/alteration (i.e., explain why the study could not be done if permission/assent/consent were required)
	
We initially conducted a pilot study to determine the feasibility of a RCT study design of BUS for NEC evaluation. While the RCT study design itself was feasible, we found that the process of obtaining consent was not practicable. The reasons why the proposed research could not be practicably carried out without the requested waiver are detailed below and in Fig 3:
 
(1) NEC is an emergency, making traditional parental consent at time of NEC concern impossible. Because NEC can rapidly deteriorate, infants with suspected NEC require “stat” evaluation with imaging and other laboratory tests. Families approached for research during emergency situations are often unable to give proper informed consent because of physical and emotional distress. Obtaining consent at time of NEC concern would also increase the risk of delaying evaluation. For these reasons, traditional parental informed consent at time of NEC concern is not possible for our study.
 
(2) Obtaining consent prior to NEC concern will require impractically large numbers to meet sample size demands. To overcome the emergency nature of NEC, we elected in our pilot study to seek consent from all infants who meet eligibility criteria, follow consented infants over time, and randomize only consented infants who develop concern for NEC. The problem with this approach is that only 36% (20/56) of consented infants developed NEC concern for randomization into the study. Based on these numbers, we will need to successfully consent 222 infants to achieve our target sample size of 80 infants. Although mathematically possible, it would require implausibly high approach and consent rates to successfully enroll 222 infants over the 2 years of the proposed study, making this approach of obtaining consent prior to NEC concern impracticable. This approach would also intrude on many families who would not need and may not

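### Section 28.3 cites a pilot SD of 9 days but states its detectable difference only at SD 8, and the number of episodes behind it is not consistent across the document

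*Combined protocol and SAP*

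**What the plan says.** Section 28.3 takes its planning values for time to full enteral feeds from the pilot study: "16 ± 9 days per episode of NEC concern". It then presents Table 1 as "sample sizes for a range of possible means and standard deviations, with significance level of 0.05 and 80% power". The columns are SD 8, 9 and 10, and the rows are differences of 4, 5 and 6 days.

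The conclusion opens with "For a 1-year study with 67 to 81 distinct episodes" and continues "for an SD of +8 days, we anticipate having sufficient sample size to detect a 5- to 6-day difference". No other conclusion is drawn from the table. Section 28.1 names the test: "days to full enteral feeds will be performed using Student's t-test".

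Two other places bear on the count:
- Addendum B, item (2) of the case for a consent waiver, argues that it would be implausible to "successfully enroll 222 infants over the 2 years of the proposed study". It says that number of consents would be needed "to achieve our target sample size of 80 infants".
- Section 8.0 sets an enrolment goal of 200 neonates (120 + 80). Its row label counts as enrolled those to be consented or those screened by chart review.

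**The concern.** A sample size said to rest on pilot data would normally be summarised at the pilot SD. Here the summary uses the most favourable of the three tabulated SDs, and the visible text does not say why the trial should vary less than the pilot. Someone reading only the concluding sentence would take 5 to 6 days as what the trial can detect. At the pilot SD, the 5-day end of that range does not have the stated 80% power with 67-81 episodes. If the trial shows no difference, the result would then be judged against a detectable difference that is somewhat too small.

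The conclusion also depends on a number of episodes that the document does not fix. The study period is one year in one place and two in another, and three different counts appear. Without one confirmed total, no statement of the detectable difference can be checked, at any SD.

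**Working it through.** **Inputs.** Significance level 0.05, 80% power, SDs of 8, 9 and 10, pilot SD 9 and 67-81 episodes are all from Section 28.3. The 80 infants are from Addendum B and the 200 neonates from Section 8.0. Assumed, because not stated: a two-sided test, 1:1 allocation, independent episodes and no loss.

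**Step 1: reproduce Table 1.** Total N = 4 × (1.960 + 0.842)² × SD² / d², where d is the difference in days.

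| Difference | SD 8: computed / printed | SD 9: computed / printed | SD 10: computed / printed |
|---|---|---|---|
| 4 days | 125.6 / 126 | 158.9 / 160 | 196.2 / 198 |
| 5 days | 80.4 / 81 | 101.7 / 102 | 125.6 / 126 |
| 6 days | 55.8 / 56 | 70.6 / 72 | 87.2 / 88 |

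All nine cells agree within 2, and rounding explains the differences. For example, 70.6 / 2 = 35.3 per arm, rounded up to 36, gives 72. The entries are therefore totals over both arms. A one-sided test does not reproduce them: it gives 64 for 5 days at SD 8, against the printed 81.

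**Step 2: read the SD 9 column.** Five days needs 102, which is 21 more than 81 and 35 more than 67. Six days needs 72, which is inside 67-81 and only just missed at the lower end.

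**Step 3: detectable difference at 80% power.** d = 2 × 2.802 × SD / √N.
- SD 8: 44.83 / √67 = 5.48 days; 44.83 / √81 = 4.98 days. This agrees with the stated 5 to 6 days.
- SD 9: 50.43 / √67 = 6.16 days; 50.43 / √81 = 5.60 days.
- Shift from SD 8 to SD 9: 0.68 day at 67 episodes and 0.62 day at 81.

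**Step 4: power at SD 9.** Power = Φ(d√N / (2 × 9) − 1.960).
- 5 days, N = 67: Φ(2.274 − 1.960) = 0.623. N = 81: Φ(2.500 − 1.960) = 0.705.
- 6 days, N = 67: Φ(2.728 − 1.960) = 0.779. N = 81: Φ(3.000 − 1.960) = 0.851.

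With the noncentral t distribution, which matches the planned Student's t-test, the results are slightly less favourable: 5.67 to 6.25 days detectable, 61-69.5% power for 5 days and 77-84% for 6 days.

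**Step 5: the other counts, at SD 9 and one episode per infant (assumption).**
- 80 infants: 50.43 / √80 = 5.64 days; power for 5 days 0.700.
- 200 infants, if all were analysed: 50.43 / √200 = 3.57 days; power for 5 days 0.975.

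The three counts therefore lead to different conclusions about a 5-day difference.

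**The case against.** Much can be said for the plan. Table 1 is right. The sentence is openly conditional on SD 8, and the SD 9 and SD 10 columns stand beside it, so nothing is hidden. Six days at SD 9 keeps 78-85% power. The stated range is loose even at SD 8, where 67 episodes give about 73% power for 5 days. The pilot SD is itself imprecise. If it came from about 16 infants (the 20 with NEC concern less the 4 not randomized, Addendum B; an assumption), its 95% interval would be roughly 6.7 to 13.9 days. That cannot separate 8 from 9, but it does not favour 8 either. All of this limits the size of the point. It does not supply the missing reason for SD 8.

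A reader might go further in either of two directions, and the documents support neither:
- **That the trial is underpowered.** This follows only if 67-81 episodes (or 80 infants) is the final total. The 200 neonates in Section 8.0 would remove the shortfall if all were analysed, but the row label there may count infants who are only screened.
- **That two years doubles the count and so cures the problem.** A total of 134-162 episodes appears nowhere in the documents. The same argument in Addendum B that gives two years also gives a target of 80 infants, which lies inside 67-81.

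**Conclusion.** The point holds in a limited form. Section 28.3 cites a pilot SD of 9, draws its only conclusion at SD 8, and shows no reason. If 67-81 episodes is the total, the conclusion at the pilot SD should be about 5.6 to 6.2 days, with 62-71% power at 5 days. This is a modest restatement and not an arithmetic error. There is no ground for inferring that Table 1 is wrong or that less favourable figures were withheld.

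The inconsistent period and counts are the more consequential part, because they decide whether a 5-day difference has about 62-71% power or, at the other extreme, about 97.5%.

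The figures rest on a two-sided test, 1:1 allocation, independent episodes, no loss and the normal approximation behind Table 1. Independence is doubtful: Section 10.2 allocates by calendar month of birth, and Section 10.7 keeps repeat episodes in the same arm. True power may therefore be lower than any figure given here.

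**What to change.** 1. Reconcile the study period (one year in 28.3, two in Addendum B) and the three counts (67-81 episodes, 80 infants, 200 neonates). State in 28.3 the one total of episodes to be analysed, and say whether the 200 includes infants who are only screened.
2. Restate the conclusion at the pilot SD for that total. If the total is 67-81 episodes, the text could read:

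> At the pilot SD of 9 days, 67-81 episodes give 80% power for a difference of about 5.6 to 6.2 days, and about 62-71% power for 5 days, assuming independent episodes (two-sided, 1:1, normal approximation as in Table 1).

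   If another total is confirmed, recompute with the same formula. For example, 200 single-episode infants would give about 3.6 days, and about 97.5% power for 5 days.
3. Keep SD 8 as a labelled optimistic scenario, or give the reason for expecting it.
4. Add that allocation by birth month, and repeat episodes kept in the same arm, may make true power lower than stated.

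**Cost.** The restatement is wording only and needs no extra patients. Step 1 does require the investigators to decide which period and count stand. The one downside is a slightly less favourable stated figure, by 0.6 to 0.7 day, if 67-81 is the total.
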